3.7.2 Statistical analysis

Exploratory data analysis will be conducted on all variables including the binary outcomes. Descriptive statistics will be generated providing proportions (percentages) for categorical data, and mean (SD)-for normally distributed data, and median (IQR) nonnormal continuous variables. A consort diagram will also be generated to show the time of enrollment, and follow-up. Bar charts showing the distribution of categorical data will also be generated. Data will be assessed for missingness especially as a result of non-follow-up in this prospective study design. In order to address this concern, a comparison of non-follow-up and those followed up will be done, and propensity scores will be constructed to use as weights in the regression models. For categorical/dichotomous outcomes, we will use Fishers Exact Test or chi-square as appropriate, and will report the respective 95% confidence intervals around point estimates, which offer important interpretation for the trial findings.

Primary outcome-1: Composite measure of consistent condom-use and use of an effective FP method. A comparison of this binary outcome will be conducted at the last follow-up. A log-

binomial regression model will be used to obtain the prevalence rate ratios (PRR) as the measure of effect or association, because the outcomes are greater than 10%. The primary exposure variable is study arm. The two intervention arms will be compared to the control arm in the same model. Potential confounders will be adjusted for, after assessing for interaction of some variables with the study-arm in the association with the primary composite outcome. Respondents from the same facility may be correlated, and so adjustment for potential clustering of observations within the selected facilities will be done.

Primary outcome-2: Incidence of any STI. Kaplan-Meier survival analysis will be conducted to determine differences in the probability of STI infection between study arms. Differences in the KM will be determined by log-rank test. Further analysis will be conducted using Poisson regression models to obtain incidence rate ratios (IRR) comparing the two intervention arms to the control arm in the same model. Potential confounders will be adjusted for, after assessing for interaction of some variables with the study-arms in the association with the incidence of STI. Adjustment for potential clustering of observations within the selected facilities will be done.

Potential confounders to be adjusted for in these analyses will include participant characteristics such as age, education level. The primary analyses are the intention to treat; for descriptive analysis, baseline data will be summarized separately by study arm. All the analysis will use STATA version 12

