1.2 Study hypothesis and Rationale

1.2.1 Study Hypotheses

We hypothesize that there will be a significantly lower incidence of HIV/STIs and increased uptake of dual protection and effective family planning methods in the intervention groups compared to the group receiving routine care i.e. we hypothesize intervention arms will be superior to routine care for our primary outcomes.

We further hypothesize that the group peer support intervention will be superior to the individual peer support arm in achieving a secondary outcome of improved self-esteem and self-efficacy (possibly mediated through improved social connectedness and a reduced sense of isolation and internalized stigma) however our study is not powered to detect the small differences we would hypothesize in our primary outcomes of STI incidence and uptake of dual protection methods between intervention arms.

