3.7 Statistical considerations and analysis plan

3.7.1 Sample size determination

Sample size determination

Sample size for this study was based on the outcomes, uptake of effective contraceptive, or prevalence of STIs, at last follow-up comparing each of the two interventions to the control in this three-arm trial. We assumed the uptake of effective contraceptives and consistent condom use as a composite outcome to be 10% [38] (in control/standard), 30% and 35% at the last follow-up in the two intervention arms. At 80% power, and 5% type 1 error rate, and a 10% loss to follow-up, the sample size in the intervention arms was 100 (each 50), while the control/standard was adjusted to 71; this follows a recommendation by Fleiss et al for multiple-arm trials that control arms have a bigger sample size than the intervention.

For the prevalence of STIs, we assumed 20%[10] in control/standard arm, 10% in the intervention-1, and 8% in intervention-2 at the last follow-up, suggesting an average of 55% reduction in prevalence of STI. With similar power of 80%, 5% type-1 error rate and 10% loss to follow-up, a total of 215 respondents in control/standard arm, and 152 per each of the intervention arms resulting in a total of 519. Since 519 respondents are sufficient to address the objectives of the uptake of effective contraceptives + consistent condom use, we determined that the final sample size for this study will be 519 (215 control/standard arm; 152 per each of the two intervention arms).

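### Does the unstated sidedness and sharing of the 5% error rate, with no named success rule, leave the trial's STI conclusion open?

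*Combined protocol and SAP*

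**What the plan says.** Section 3.7.1 describes the sample size as "comparing each of the two interventions to the control in this three-arm trial". For STI it assumes 20% under routine care, 10% in one intervention arm and 8% in the other, "suggesting an average of 55% reduction in prevalence of STI". The sizes follow "With similar power of 80%, 5% type-1 error rate and 10% loss to follow-up": 215 under routine care and 152 in each intervention arm, 519 in all.

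Section 3.7.2 names Fisher's exact or chi-square tests for categorical outcomes and adds that the analysts "will report the respective 95% confidence intervals around point estimates". For the condom and contraception composite it specifies a log-binomial model and says "The two intervention arms will be compared to the control arm in the same model". For STI it says "Differences in the KM will be determined by log-rank test". It then introduces, as further analysis, "Poisson regression models to obtain incidence rate ratios (IRR) comparing the two intervention arms to the control arm in the same model". It gives no test level, sidedness or multiplicity rule.

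Three other places bear on what would count as success:
- In section 1.2.1 the investigators write "we hypothesize intervention arms will be superior to routine care for our primary outcomes".
- Objectives 2.2 and 2.3 set out to describe and compare each outcome by arm, separately.
- Section 6.2 says the team will seek resources for scale-up if one or both interventions are acceptable and feasible and improve both uptake and STI incidence.

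**The concern.** A 5% error rate for two comparisons with a shared control can mean one-sided 5% each, two-sided 5% each, or 5% split between the arms. The arm sizes could have shown which was meant, but each of the three can be paired with one of the planned STI effects so that it comes close to 215 and 152. The risk of wrongly declaring an STI benefit, and the power, would then rest on a choice nobody wrote down.

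Two further gaps appear to add freedom. The log-rank test could be a single three-arm test or two pairwise tests, and the Poisson model might give a different answer. Success might need one arm or both, and one outcome or both. If all this were settled after the data were seen, the investigators could pick the most favourable route.

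**Working it through.** **Inputs.** From section 3.7.1: STI 20% versus 10% or 8%, average 9% (a 55% reduction: 20% × 0.45 = 9%); power 80%; loss 10%; sizes 215/152/152. The ratio 215/152 = 1.414 is √2, so I take k = 1/√2 intervention participants per control participant.

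**Plan's own sizes.** I use the usual pooled two-proportion formula:

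n(control) = [z_α √(p̄(1−p̄)(1+1/k)) + z_β √(p₁(1−p₁) + p₂(1−p₂)/k)]² / (p₁−p₂)²

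Here p̄ = (p₁ + k p₂)/(1 + k), z_β = 0.842, and every reading is divided by 0.9 for loss.

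| Reading of the 5% | Effect | z_α | Control / arm before loss | After loss, rounded up |
|---|---|---|---|---|
| One-sided, per comparison | 20% v 10% | 1.645 | 191.7 / 135.6 | 214 / 151 |
| Two-sided, per comparison | 20% v 9% | 1.960 | 196.6 / 139.0 | 219 / 155 |
| Two-sided, split over the arms | 20% v 8% | 2.241 | 195.3 / 138.1 | 218 / 154 |
| Two-sided, per comparison | 20% v 10% | 1.960 | 244.5 / 172.9 | 272 / 193 |
| Two-sided, per comparison | 20% v 8% | 1.960 | 160.6 / 113.6 | 179 / 127 |

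The first three rows come within 4 participants of the stated 215 and 152, about 2%; the last two do not fit. Multiplying by 1.1 for loss brings the second and third rows closer (217/153 and 215/152) but moves the first away (211/150). Each of the first three readings also needs a different effect, so they are not one design at three error rates. Other standard formulas can be made to fit more than one reading, so the sizes alone do not identify the one used.

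**False STI benefit.** If neither intervention works, the two test statistics share the control arm and correlate at 152/(152 + 215) = 0.414. The chance that at least one arm shows a false benefit is 1 − P(Z₁ < c, Z₂ < c):
- c = 1.645 (one-sided 5%): 9.0%
- c = 1.960 (two-sided 5%): 4.6%
- c = 2.241 (two-sided 2.5%): 2.4%

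At two-sided 5% each arm carries 2.5% in the beneficial direction, so the sum cannot exceed 2 × 2.5% = 5%. Counting a false difference in either direction, the three figures are 18.0%, 9.3% and 4.7%.

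**Which reading the text supports.** A 95% interval corresponds to a two-sided 5% test of a single comparison. Chi-square and log-rank tests are ordinarily non-directional. Section 3.7.2 mentions no one-sided test, no 2.5% level and no 97.5% interval. An analyst following it would test each arm against routine care at two-sided 5%.

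**Power on that reading.** Evaluable numbers are 215 × 0.9 = 193.5 and 152 × 0.9 = 136.8. Power is Φ{[(p₁−p₂) − 1.960 SE₀]/SE₁}, with SE₀ pooled and SE₁ unpooled:
- 20% v 10%: SE₀ 0.0408, SE₁ 0.0385, z = 0.52, power 70%
- 20% v 9%: SE₀ 0.0404, SE₁ 0.0378, z = 0.82, power 79%
- 20% v 8%: SE₀ 0.0399, SE₁ 0.0369, z = 1.13, power 87%

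The stated 80% therefore matches the average effect that section 3.7.1 itself cites.

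**The case for a change.** The strongest case for a change is that every omission is real and wording alone would close it. The intervals are mentioned in the sentence on Fisher and chi-square tests, and no decision is tied to them. Naming the deciding STI test would also rule out a later choice between log-rank and Poisson. That much stands: a sentence on sidedness and level would make a tidier plan.

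The argument on success rules is weaker. Suppose section 6.2's two outcome conditions and section 1.2.1 are treated as rival rules. Simulated at the planned effects (STI 20/10/8%, composite 10/30/35%) and two-sided 5%, section 6.2's conditions are met in 93.0% of trials. Section 1.2.1, read as requiring both arms and both outcomes, is met in 65.5%. The difference, 93.0 − 65.5 = 27.5 points, would be trials where the two disagree. But section 1.2.1 states a hypothesis and section 6.2 describes work with the Ministry and donors. Neither is offered as a test of success, and section 1.2.1 does not say that all four comparisons must succeed. The simulation also treats condom and contraceptive uptake as independent of STI within a participant, which is hard to believe.

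On the log-rank test, section 3.7.2 puts it first and calls the Poisson model further analysis, so an order can be inferred. A three-arm test used as a gate would lower the false-benefit chance from 4.6% to 2.2%, but the plan mentions no gate.

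On multiplicity, some statisticians would adjust for two interventions sharing a control. Others would not when each intervention answers its own question. Section 3.7.1 frames the design as each intervention against control, which is consistent with the second view.

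**Conclusion.** No change is needed. Read in the ordinary way, as two-sided 5% for each arm against routine care, the plan limits the chance of a false STI benefit in some arm to 4.6%, or 9.3% if harm is counted too. The 9.0% figure needs a one-sided test that the documents nowhere describe. Following section 3.7.2 as written has not been shown to give a wrong answer. What is missing is detail that an analyst fills sensibly, together with a multiplicity choice on which practice differs.

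The conclusion assumes that the 95% intervals signal the working level and that the log-rank result leads for STI. The error rates use a normal approximation without covariate, clustering or weighting adjustment, and they cover STI only. Across both primary outcomes the four comparisons cap the chance of any false benefit at 4 × 2.5% = 10%. A reader should also take the 80% power as referring to the average STI effect; for the arm assumed to reach 10% it is about 70%.

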The HBM was spelled out in terms of four constructs representing the perceived threat and net benefits: perceived *susceptibility*, perceived *severity*, perceived *benefits*, and perceived *barriers*. These concepts were proposed as accounting for people's "readiness to act." An added concept, *cues to action*, would activate that readiness and stimulate overt behavior. A recent addition to the HBM is the concept of *self-efficacy*, or one's confidence in the ability to successfully perform an action. This concept was added by Rosenstock and others in 1988 to help the HBM better fit the challenges of changing habitual unhealthy behaviors, such as being sedentary, smoking, or overeating.

In the intervention arms, the peer educators will be explicitly trained to use the Health Belief Model and assist their peers to explore perceived susceptibility, perceived severity, perceived benefits, perceived barriers and self-efficacy with the aim of adopting healthier behaviors.

These peer mothers will offer individualized support and education to their assigned adolescents during study visits scheduled together with their routine clinic visits. The design of the individualized peer intervention arm builds on prior pilot work by MUJHU researchers in the Mulago PMTCT program. In 2012 the team completed an implementation science study providing individual peer support by "Family Planning (FP) Champions" to support uptake of family planning among newly delivered mothers. This pilot FP intervention showed increased uptake of FP services from 33% prior to the peer FP intervention to 61% among women during the intervention and 45% post intervention[29]. This preliminary work provides support for testing the one-to-one peer intervention in a randomized implementation study.

The peer educators selected will be young mothers who have successfully taken up contraception or dual methods (including consistent condom use) postpartum themselves who can thus serve as both peers and positive role models.

Study design, study population and setting

The MUJHU Clinical Research Site (CRS) under the Johns Hopkins University Clinical Trial Unit (JHU CTU) research scope includes primary prevention of HIV and reproductive health. This NIH sponsored **HI-4-TU** MUJHU Study is an adolescent focused implementation science study directed at improved social support and dual prevention of both HIV/STI's and subsequent unplanned pregnancies.

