The intended study population is 519 currently pregnant adolescents (without diagnosed pregnancy related complications or serious co-morbidity) who are attending antenatal care in Kampala and are aged 15 to 19 years at enrollment with follow-up through 6 to 9 months after delivery.

We will use a randomized study design to test the acceptability and effectiveness of two enhanced peer lead, reproductive health promotion interventions compared to routine health care. The study participants will be individually randomized to one of three arms.

- Routine Care (Arm 1): Group education and counseling from ANC clinic midwives, routine PMTCT services including routine HIV C&T and family planning and partner C&T services for those requesting it.
- Intervention Arm Two: Routine Care plus group peer education and support beginning every 4 weeks post enrollment to delivery and at 6 and 10 weeks, 3, 6 and 9 months post-delivery.
- Intervention Arm Three: Routine Care plus individual peer education and counseling beginning every 4 weeks post enrollment to delivery and at 6 and 10 weeks, 3,6 and 9 months post-delivery.

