3.2 Study Setting and population

3.2.1 Study Setting

The study will enroll participants from Mulago National Referral hospital antenatal clinics in Kampala. If recruitment at Mulago hospital is insufficient (due to the current ongoing hospital rehabilitation works), we will recruit patients from the Uganda China Friendship hospital, Naguru in Kampala, KCCA Clinics including Kisenyi Health Center IV, Komamboga health center III, Kawaala Health center III and Kiswa Health Centre III and/or Nsambya hospital. All these hospitals have established PMTCT programs and see a substantial number of pregnant adolescents in their antenatal care clinics and they provide PTCT services and group education sessions in the ANC and PNC Clinics on maternal and child health as part of routine care.

In order to prevent cross-contamination between the control and intervention arm populations, the group education and counseling sessions will take place at the MU-JHU Research premises. All other routine and individual peer support and education services will take place on site at the health care facility providing ANC and PNC services.

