Routine care in ANC/PNC clinics varies within hospitals/health centers depending on available resources and also among healthcare providers; hence the standard of care described above is not what is provided. The basic minimum that is usually provided is obstetric care, delivery plans and health education which is not standardized and there may be stock-outs of essential laboratory commodities and pharmacy hours are restricted. In practice even at the national referral hospital it is not uncommon for pregnant women not to receive Hemoglobin, syphilis or urine screening tests (as confirmed by triangulated data from women's self-reports in AIS 2011. [6])

The routine care group (control Arm 1) will have their visits conducted in the ANC/PNC clinic following the usual care as provided in these clinics, as summarized above.

The intervention groups will also have the routine care as provided within Mulago hospital or the designated health facility and in addition will have the enhanced interventions which will focus on providing support and education including reproductive health information to the pregnant and postnatal adolescents on their risk of HIV/STI acquisition, and condom use utilizing adolescent friendly IEC materials and interactive exchanges either in a group or one-

to-one. They will also receive counseling on the importance of family planning and those interested will be referred to the family planning clinic for provision of their choice of the effective available family planning methods. In addition, the interventions will also provide education on the importance of delivery in a hospital, post-natal care, infant feeding and importance of immunization for the baby. Both enhanced intervention groups will receive pre appointment reminders of follow up appointments through sms or phone calls if they agree. The adolescent group education counseling sessions will be done by trained, experienced peer educators during around 6 sessions conducted in the MU-JHU clinic. The one-to-one peer support and education counseling sessions will occur in the ANC for pregnant adolescents (in different clinic space from the routine care group) and postpartum the sessions will be held in the adolescent clinic (ward 15) in Mulago Hospital. The enhanced intervention sessions will occur in different places from each other and from the control group so as to minimize cross-contamination between the groups.

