	Urine	 Collect Urine (20mls) 
  Rapid test for Gonorrhea infection  Rapid test for Chlamydia infection
	Pelvic	
 • Collect vaginal swab for rapid Trichomonas vaginalis testing • Collect swab for Bacterial vaginosis testing (PH, Whiff and Clue cells)

Enhanced Peer Support Education and Counseling (Intervention)	Depending on the group the participant is randomized to, the intervention will be done around 4 weeks after enrolment as this is logistically appropriate for the study. Participants in Arm 2 will be put in homogenous groups (similar gestation, age group and language preference) of 8 – 12 adolescents, while the Arm 3 participants will schedule their individual follow-up visits on the same day as their clinic visits. Participants in the Control Arm will receive routine antenatal, delivery and follow-up services with next study visit at 3 months postpartum
Qualitative component	Participants preselected for the serial IDIs and FGDs will have the baseline interviews and FGDs within 3 weeks of enrolment prior to receiving the intervention

The participant will be provided with an appointment card (usual cards used in the ANC/PNC clinics) however a round colored sticker (different colors for each study arm) will be placed on the card to differentiate the 3 study groups.

STI treatment will be provided for any curable STI diagnosed at screening and in follow-up for the participant and her partner/s in accordance with national treatment algorithms.[33-34] Participants found to be HIV positive (by two separate rapid tests) will not be excluded from this proposed study but will be counseled, encouraged to disclose to their partner/s and will receive PMTCT services including Option B+ with ARV treatment for life as per national guidelines. As part of PMTCT services they will be encouraged to invite their partner/s for HIV C&T and their HIV-exposed infants will be followed up with linkages to ongoing services. Participants with positive syphilis tests will be treated and have repeat testing done per local national guidelines and also at the final visit.

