4 ANTICIPATED CHALLENGES AND MITIGATION PLANS

4.1 Maintaining Long –Term cohesion among peers

This will depend on the individual stability of the members, the group leader capability, and the quality of their relationships. This will require close monitoring and support by the group leaders and peer educators. We will ensure that there is continuous training, counseling and ongoing support sessions to address issues as they arise and support long-term cohesion including an understanding and commitment of protecting each other's privacy and not sharing confidential disclosures outside the group.

4.2 Stigma and discrimination:

HIV-related stigma and discrimination continue to be important issues in Uganda. MUJHU may be perceived as being associated with HIV research; so participants attending MUJHU may be suspected by others of being HIV-infected (despite many HIV-uninfected persons attending MUJHU). MUJHU will consult with youth and attempt to mitigate against this risk by rebranding and marking the lower building ground floor which has a separate entrance and exit as a

Youth-Friendly Service. Clinic services for teens will be on the ground floor and separated from other clinic and study populations.

4.3 Vulnerability of pregnant and postpartum women to relocate:

The time immediately after delivery may be associated with geographic displacement as many new mothers move for several weeks or months to their village of origin after delivery both because of the care needed by the new infant (and mother) and Uganda cultural norms among several tribes. We will attempt to minimize this through exploring this theme in our FGDs as well as our screening and enrollment procedures inquiring about intentions to remain within 30Kms of the clinic and encouraging women to advise of any temporary or permanent change in residence and maintain contact with the study team. We will also maintain regular contact with participants through their scheduled visits and by phone calls/sms using agreed general language with no mention of HIV or MUJHU).

4.4 Male partner and family involvement:

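### Clustering is adjusted for by recruiting facility only, so correlation from shared delivery in the Arm 2 peer groups is left out of both primary analyses

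*Combined protocol and SAP*

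**What the plan says.** Allocation is by person: "The study participants will be individually randomized to one of three arms" (Section 1.1). Delivery in Arm 2 is by group. Table 2 in Section 3.5 says "Participants in Arm 2 will be put in homogenous groups (similar gestation, age group and language preference"), with 8 to 12 adolescents in each. Section 3.4.6 has these sessions led by "trained, experienced peer educators during around 6 sessions conducted in the MU-JHU clinic", and Section 3.2.1 confirms that "the group education and counseling sessions will take place at the MU-JHU Research premises", whichever facility recruited the participant.

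For Arm 3, Section 1.1 says: "These peer mothers will offer individualized support and education to their assigned adolescents". The number of peer mothers and their caseloads are not given.

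Section 3.7.2 names one source of correlation, the facility: "Respondents from the same facility may be correlated, and so adjustment for potential clustering of observations within the selected facilities will be done". That sentence belongs to the condom and contraception composite. A similar one closes the STI paragraph, after the Poisson model. No adjustment method is named in either place. For the survival curves the plan is: "Differences in the KM will be determined by log-rank test". Fisher's exact or chi-square tests are planned for categorical outcomes. Section 3.7.1 contains no ICC and no design effect.

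Mulago is the default recruiting site. Other facilities join only if its recruitment falls short (Protocol Summary; Section 3.4.1).

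**The concern.** This is a partially nested design: outcomes in Arm 2 may correlate within peer groups, while controls share no group. The protocol gives a reason to expect some variation between groups. On long-term cohesion, Section 4.1 says: "This will depend on the individual stability of the members, the group leader capability, and the quality of their relationships".

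Facility is the wrong level for this. Arm 2 groups are formed on gestation, age and language and meet centrally, so they need not follow facility lines. With Mulago alone there is one facility and nothing to adjust for. An ordinary log-rank, Fisher or chi-square test does not account for peer group either.

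If shared delivery does produce correlation, the standard error of the Arm 2 contrast is too small. The test then rejects more often than the stated 5%, and STI power is below its unclustered value. The error favours declaring the group intervention effective, and Section 6.2 ties scale-up to these contrasts. If peer-group membership is not recorded, the problem may not be repairable at analysis.

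**Working it through.** **Inputs.** From Section 3.7.1: 215 control and 152 per intervention arm, 10% loss, 5% type I error (sidedness not stated), 80% power, and STI proportions of 20% (control), 10% and 8% (interventions), described as an average 55% reduction, i.e. 20% against 9%. From Section 3.5: groups of 8 to 12, so 152/12 to 152/8, or about 13 to 19 groups. Assumed, because the documents give none: ICC 0.01 to 0.05.

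**1. The plan's own figure.** I used the pooled two-proportion formula with an intervention-to-control ratio of 152/215 = 0.707 and division by 0.9 for loss.
- 20% against 10%, one-sided 5%: 192 and 136 evaluable, then 214 + 152 + 152 = 518.
- 20% against 9%, two-sided 5%: 197 and 140 evaluable, then 219 + 156 + 156 = 531.

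Both are within 3% of the stated 519, and neither contains a clustering term. Two-sided 20% against 10% does not reproduce it (273 and 194 per arm).

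**2. Evaluable numbers.** Control n0 = 215 × 0.9 = 193.5. Arm 2 n1 = 152 × 0.9 = 136.8. Group size m = 8 × 0.9 = 7.2 to 12 × 0.9 = 10.8.

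**3. Type I error if the correlation is ignored.** DE = 1 + (m − 1) × ICC, applied to Arm 2 only. With r = √[(1/n0 + 1/n1) / (1/n0 + DE/n1)], the two-sided error under a zero average effect is 2 × [1 − Φ(1.96r)].

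For m = 10.8 and ICC 0.05: DE = 1.49; r = √(0.012478/0.016060) = 0.8815; 1.96r = 1.728; error = 8.4%.

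| Planned group size (evaluable) | ICC 0.01 | ICC 0.02 | ICC 0.05 |
|---|---|---|---|
| 8 (7.2) | 5.4% | 5.8% | 7.1% |
| 10 (9.0) | 5.5% | 6.1% | 7.8% |
| 12 (10.8) | 5.7% | 6.3% | 8.4% |

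**4. STI power.** Power = Φ[(p0 − p1 − 1.96 × SE0)/SE1], where SE0² = p̄(1 − p̄)(1/n0 + DE/n1) and SE1² = p0(1 − p0)/n0 + DE × p1(1 − p1)/n1. A second version replaces n1 by n1/DE throughout. The ranges below span the two versions, for ten per group (DE 1.09 and 1.45), two-sided.

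| Contrast | Unclustered | ICC 0.01 | ICC 0.05 |
|---|---|---|---|
| 20% vs 10% | 69.8% | 67.2-67.6% | 57.7-59.5% |
| 20% vs 9% | 79.3% | 76.9-77.3% | 67.7-69.6% |
| 20% vs 8% | 87.1% | 85.1-85.5% | 77.0-78.8% |

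The loss is about 2-3 points at ICC 0.01 and 8-12 points at 0.05. With nine evaluable per group, the loss at 0.05 is about 7-11 points. One-sided, 20% against 10% goes from 80.3% to 78.6% and 72.0% (first version). Section 3.7.1 does not say which arm is intervention-1, so any row may apply to Arm 2. For the composite (10% against 30%), power stays near 98% at ICC 0.05, so the issue there is the standard error, not power.

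**5. Simulation check.** With 194 controls, 14 groups of 10, a true rate of 20% and no average effect, the unadjusted test rejected 4.9%, 5.8%, 6.1% and 8.2% of the time at ICC 0, 0.01, 0.02 and 0.05. A group-level test held 4.9% to 5.5%.

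**6. Sorting alone.** When groups were sorted on a prognostic covariate with no group effect, the unadjusted test rejected 5.0%. A clustered test without the covariate rejected 2.3%, and with it 4.4%. With sorting plus a group effect at ICC 0.05, the figures were 7.2%, 2.9% and 4.8%.

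**The case against.** **The size is assumed.** This stands. At ICC 0.01 the effect is minor. Because groups are formed after individual randomisation, there is no inflation if peer support changes nobody's outcome. The inflated error rates need a zero average effect together with real differences between groups. At a 20% STI rate, ICC 0.05 means a between-group SD of √(0.2 × 0.8 × 0.05) = 8.9 points, with about 95% of groups between roughly 6% and 40% under a beta model. ICC 0.05 is therefore an upper planning value.

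**The protocol limits variation in delivery.** Section 4.1 itself promises continuing training and support, Section 3.4.6 has formal training and similar messages in both intervention arms, and Section 3.4.6.2 adds curriculum training and regular mentoring. These argue for a low ICC, not for leaving the level out.

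**Arm 3.** A reader might infer the same or larger inflation there, since a peer's caseload could exceed a group's size. The documents do not support a figure: they give neither the number of peers nor the caseload, and do not say whether assignment stays fixed. One-to-one sessions also involve no interaction between participants. Section 3.2.1 places individual support at the recruiting facility, so with several sites facility adjustment might absorb part of it, although Section 3.4.6 moves the postpartum sessions to Mulago.

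**Log-rank.** The closing facility sentence can be read as covering the whole STI paragraph. Even so, no method is named, and facility is still not peer group.

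**Baseline power.** A reader might attribute all of the gap between 80% and the lower power figures to clustering. The 70% starting value for 20% against 10% comes from two-sided testing, which is a separate sample-size question.

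**Conclusion.** The concern holds for Arm 2. The plan's clustering adjustment is at a level that does not capture the peer groups and has no effect with a single facility. The log-rank and Fisher/chi-square tests share the gap.

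The omission is certain; its size is not. Given an assumed ICC of 0.01 to 0.05 and about 7 to 11 evaluable per group, type I error is about 5.4% to 8.4%. STI power is lower by roughly 2-3 to 8-12 points, the upper figures being for groups of ten at ICC 0.05. With no shared-delivery correlation the planned test is valid. Point estimates are not biased in either case.

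For Arm 3 the concern is conditional on each peer mother keeping a fixed caseload, and no figure should be attached.

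A reader might also infer that matching groups on age, gestation and language itself inflates the error. It does not: only correlation from shared delivery does. The point is worth fixing, but it does not show that the trial's conclusions would be wrong.

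**What to change.** 1. **Record** peer-group ID and peer-educator ID on the case record form, and language preference if it is not already collected.
2. **Both primary models:** replace the facility-clustering sentences with a partially nested analysis.
   - Enter facility as a fixed effect if there is more than one.
   - Include age group, gestation and language as covariates in all arms.
   - Use a small-sample-corrected cluster-robust variance by Arm 2 peer group, with controls as singletons.
   - If the log-binomial model does not converge, use modified Poisson with robust variance.
   - In Arm 3, cluster by peer educator as the primary approach only if there are enough peers; otherwise do so as a sensitivity analysis.
   - Under intention to treat, keep each participant in her first assigned group (or with her first assigned peer) and treat those never placed as singletons.
3. **STI outcome:** base inference on the cluster-adjusted model. Make the log-rank and Fisher/chi-square tests descriptive, or replace them with cluster-adjusted versions.
4. **Section 3.7.1:** state that the sample size assumes ICC = 0, and show the effect over ICC 0.01 to 0.05.

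The cost is revised wording in Sections 3.7.1 and 3.7.2 and two or three data fields, with no added participants or visits. Intervals will be somewhat wider. If the group-forming covariates are left out, the analysis over-corrects: 2.3% rejection instead of 5% in the simulation above.
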